The MCCG, a robotic magnetic capsule guidance system, was provided by Ankon Technologies Co. Ltd (Shanghai, China). The MCCG system was consisted of a guidance magnet robot, a capsule endoscopy, a data recorder and a computer workstation with a software for real-time view and two joysticks for capsule orientation control. The guidance magnet robot was of C-arm type with five degrees of freedom: two rotational (horizontal and vertical directions) and three translational (forward/backward, up/down, left/right).

After a standardized gastrointestinal (GI) preparation regimen for MCCG, patients were placed in the left lateral decubitus position and swallowed MCCG-1 or MCCG-2 with a small amount of water according to a random number table with the help of nurses at the digestive endoscopic center. When MCCG reached the stomach, it would be lifted away from the posterior wall, rotated and advanced to the fundus and cardiac regions, followed by the gastric body, angulus, antrum and the pylorus. During this procedure, position changes such as supine, prone, left and right lateral were also helpful in achieving clear observation and smooth transition. Standardized examination procedure of MCCG was available online at videogie.org¹⁰. Cases with suspected malignancy were rechecked under conventional endoscopy.

Image capture rate in the esophagus and stomach were 2 fps or 6 fps in MCCG-1 or MCCG-2 group, and standardized operation of MCCG were performed twice for complete gastric examination. After the capsule moved into the duodenum, patients left the hospital with the data recorder to continue with small-bowel examination. In the small bowel, MCCG-2 offered an adaptive frame rate technology which adjusted the image capture rate based on how fast the capsule was moving.

Study outcomes and definition

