Basic characteristics of the enrolled patients were prospectively collected. Primary study outcome was efficacy analysis including visualization of the esophagus and duodenum indicated by detection rate of Z-line and duodenal papilla defined as at least one image of Z-line or duodenal papilla was obtained, the number of images captured for esophagus and Z-line, circumferential visualization of Z-line as the number of quadrants observed and cleansing level of Z-line as bubbles/saliva on Z-line¹¹. Operation related parameters included esophageal transit time (ETT), gastric examination time (GET), gastric transit time (GTT), small bowel transit time (SBTT) and total running time (TRT). Image quality,

maneuverability and detection of lesions were also prospectively documented. Any procedure related adverse events were closely recorded.

GET was defined as the time for examination of gastric primary anatomical landmarks twice. Image quality ranged from one to ten denoting from the worst to the highest¹². Maneuverability was classified as fluency (the response to operation and video effect), stability (the ability of holding the capsule at one position for at least one minute) and comfortableness (the operator's fatigue degree during the examination), and each index graded from one to five with one as the worst and five as the best.

All examinations and maneuverability evaluation were performed by an endoscopist ([name]) with an experience of more than 1000 cases of MCCG operation. Two other endoscopists blinded to the grouping would independently evaluate the image quality with a mean value as the final score, and a third endoscopist would make the final judgement when there existed a discrepancy more than three. The randomization schedule was generated by the investigator using a random number table, making it possible that patients enrolled and endoscopists involved were all blinded to the treatment protocol assigned.

Statistical analysis

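### The only adverse events the plan provides for recording are procedure-related ones, so an unassigned judgement of relatedness comes before collection and other events may leave no record

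*Combined protocol and SAP*

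**What the plan says.** Safety collection is a single sentence in METHODS, Study outcomes and definition: "Any procedure related adverse events were closely recorded". The document does not define an adverse event or procedure-related, and it does not say who decides relatedness, by what criteria, or over what period. No other section provides for recording events whatever their cause.

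On blinding, the Study design section calls the trial blinded. The paragraph on randomisation says "The randomization schedule was generated by the investigator using a random number table". It then presents this as the means by which blinding was achieved: "making it possible that patients enrolled and endoscopists involved were all blinded to the treatment protocol assigned". A separate statement covers one outcome: "Two other endoscopists blinded to the grouping would independently evaluate the image quality". No matching statement exists for adverse events.

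Four other statements bear on who could know the arm:
- Study intervention: patients "swallowed MCCG-1 or MCCG-2 with a small amount of water according to a random number table with the help of nurses".
- Study intervention: the system includes "a computer workstation with a software for real-time view and two joysticks for capsule orientation control".
- Study intervention: "Image capture rate in the esophagus and stomach were 2 fps or 6 fps in MCCG-1 or MCCG-2 group".
- Study outcomes and definition: "All examinations and maneuverability evaluation were performed by an endoscopist", and the fluency grade given by that endoscopist includes how the video looked.

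The Statistical analysis section gives a general test for categorical variables. It names no safety comparison, and it states that no sample size was calculated.

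**The concern.** The qualifier sits on what is recorded, not on what is later reported. Staff who follow the sentence have no instruction to write down an event they think unrelated. That judgement is often uncertain here. Patients may enter with abdominal complaints, so new pain or nausea can be put down either to the capsule or to the existing condition. The plan also does not say whether the preparation, the position changes, or the hours of small-bowel transit after leaving hospital count as part of the procedure.

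Two things are at stake. The first does not depend on blinding: events are lost at collection, and neither their number nor their nature can be recovered from the trial dataset. The second does depend on it: if the person judging relatedness knows which capsule was given, the filter might act differently in the two arms, and tables by arm would then mix the capsules' safety with the assessor's habits.

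**Working it through.** The plan gives no safety figure to reproduce. The main check is therefore textual, and the arithmetic only illustrates size.

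**1. Order of steps.** The recording sentence covers procedure-related events. To apply it, someone must classify the event first. Nothing elsewhere adds a step that records events before classification.

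**2. Who could know the arm.** Set side by side:

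| Role | What the protocol says | Stated as blinded? |
|---|---|---|
| Patients | Swallow the assigned capsule | Yes |
| Operating endoscopist | Live view at 2 or 6 fps (6/2 = 3-fold); grades fluency, including video effect | Yes, but doubtful |
| Nurses | Help give the capsule according to the random number table | Not mentioned |
| Investigator | Generated the schedule | Not mentioned as such |
| Two image readers | Score image quality | Yes, for that task |

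The person who attributes adverse events appears nowhere. Knowledge of the arm at attribution is thus possible but not documented.

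**3. What zero recorded events would mean.** Input from the protocol: 80 patients at 1:1, nominally 80/2 = 40 per arm. The zero count is hypothetical. The exact two-sided 95% upper limit for 0/40 is

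1 − 0.025^(1/40) = 0.088, or 8.8%.

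This bounds the rate of recorded events. If a share *s* of patients with any event has it attributed and recorded, the limit for any event is roughly 0.0881/*s*. The shares are assumptions; the documents give none.

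| Assumed share *s* | Approximate upper limit, any event |
|---|---|
| 0.8 | 0.0881/0.8 = 11% |
| 0.5 | 0.0881/0.5 = 18% |
| 0.3 | 0.0881/0.3 = 29% |

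These figures count events of any cause, including truly unrelated ones. They do not measure harm from the capsule.

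**4. When the comparison between arms would be distorted.** Assume a true event rate of 10% in both arms, so 40 × 0.10 = 4 events are expected per arm.
- Equal attribution, 80% in each: 4 × 0.8 = 3.2 against 3.2, ratio 1.0. Events are lost but the ratio is unchanged.
- Unequal attribution, 80% against 40%: 3.2 against 4 × 0.4 = 1.6, ratio 0.5 with no true difference.

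The distortion comes entirely from the assumed gap in attribution.

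**5. Could that produce a significant result?** With 40 per arm, Fisher's exact test gives p = 0.055 for 0 against 5 events and p = 0.026 for 0 against 6. Under the unequal scenario (recorded rates 0.10 × 0.8 = 8% and 0.10 × 0.4 = 4%), summing the binomial probabilities of all tables with p < 0.05 gives about 2.4%. A spurious significant difference is unlikely. The practical risk is a misleading descriptive table.

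**The case against.** The strongest case on the other side has four parts.

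- **Blinding is stated.** The protocol says patients and endoscopists were blinded, and no sentence says that an unblinded person attributes events. A reader might infer that the filter is applied by someone who knows the capsule and so biases the safety comparison. The documents do not support that. They give grounds to doubt the operator's blinding, but do not say that the operator or the nurses attribute events. Both arms also share the guidance system, preparation and standardised operation, and nothing in the text suggests a reason to attribute events differently. This part stands, and it limits the point to a possibility that cannot be excluded.
- **No safety comparison is planned.** The primary outcome is visualisation, and no safety hypothesis or test is named. This stands too: it would be wrong to say that a planned comparison is compromised. Counts of events by arm remain a natural output of a randomised trial of two devices.
- **The sentence is a short summary.** It does not forbid recording other events, and the case report form is not described. This stands as a caution on reading the sentence as a ban. It does not supply the missing provision, because the protocol is where the scope of collection should be stated.
- **The magnitudes rest on assumed inputs.** True of the attribution shares and event rates. The 8.8% limit needs only the 40 per arm and a zero count.

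None of this answers the loss of unattributed events, which occurs under perfect blinding as well.

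**Conclusion.** The point holds in limited form. As written, the plan provides for recording only events already judged procedure-related, by an unnamed person under unstated criteria. Unattributed events need not be kept, so a clean safety record would mean that nothing was attributed. For 0/40 the upper limit is 8.8% for recorded events. The 11% to 29% range for any event rests on assumed shares of 80% down to 30%.

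Bias between the arms is not shown. It would require both an assessor who could tell the arm and a judgement that differs by arm; the documents make the first plausible and are silent on the second. The conclusion also rests on reading the recording sentence as the complete collection rule; a case report form that already captures all events would remove most of the concern. The change is worth making because it is cheap and the lost information may not be recoverable at analysis. It affects no sample size or significance level.

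**What to change.** Replace the recording sentence with wording such as: *All adverse events from swallowing of the capsule onward are recorded, whatever their suspected cause. Relatedness is assigned afterwards from a written description that does not reveal the arm, by one of the endoscopists already serving as blinded image readers. All events, and then related events, are tabulated by randomised arm.*

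The description should carry no identifier that links it to images the reader has scored. Simple counts by arm are enough; no test needs to be added.

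The cost is one protocol sentence, one case-report line and a little reader time. The small downside is that some trivial unrelated complaints will be recorded. If collection has already finished under the existing rule, the report should say that only events attributed to the procedure were recorded and who made that judgement, and should not describe the result as an absence of all adverse events.

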Second-Generation Magnetically Controlled Capsule Gastroscopy with Improved Image Resolution and Frame Rate: Study Protocol for A Randomized Controlled Clinical Trial

Document Date: February 1st, 2019.

Trial registration: ClinicalTrials.gov ID: NCT03977935

INTRODUCTION

Magnetically controlled capsule gastroscopy (MCCG) provides good visualization of the stomach, and is highly accepted due to the characteristics of painlessness, noninvasiveness and favorable diagnostic accuracy as conventional endoscopy^{1,2}. However, the upper gastrointestinal (UGI) tract under capsule endoscopy (CE) continues to present challenges including rapid transit through esophagus and duodenum^{3,4}, as well as longer gastric examination time⁵ compared to conventional endoscopy. Technical improvements in frame rate, field of view, dual camera, image resolution and battery life have been performed to optimize the clinical application of CE, and some turned out to be effective^{6,7,8,9}.

Therefore, a new-generation MCCG (MCCG-2) highlighted with a higher and adaptive frame rate of 8 frames per second (fps), better image resolution of 720 x 720 pixels, wider field of view of 150°, extended battery life of more than 12 hours and anti-jamming wireless data transmission has been developed. Hence, this pilot study was conducted to determine whether MCCG-2 can further optimize the visualization of UGI tract, thus result in better diagnosis of UGI diseases.

METHODS

Study design

This pilot study was a prospective, single-centered, blinded randomized controlled study, approved by the institutional review board of Shanghai Changhai Hospital and registered at ClinicalTrials.gov. with registration number NCT03977935. Written informed consent was obtained from each enrolled subject.

Patients

From May 2019 to June 2019, 80 consecutive patients aged 18-80 years with or without abdominal complaints referring for MCCG examination were prospectively enrolled and randomly allocated into MCCG-1 group or MCCG-2 group a 1: 1 ratio. Patients with any of the following contraindications for MCCG were excluded: pacemakers or electromedical devices implanted which are incompatible with magnetic field; suspected or known gastrointestinal stenosis, obstruction or other known risk factors for capsule retention; scheduled magnetic resonance imaging examination before excretion of capsule; pregnancy or suspected pregnancy; and any other contraindications determined by endoscopists.

Study intervention

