As a pilot study to evaluate the clinical utility of MCCG-2, sample size was not calculated for this study. Quantitative data were summarized with parametric statistics, mean and standard deviation, or with nonparametric statistics, median and interquartile range, whereas categorical data were presented as frequency (percentage). Data with a normal distribution were compared using parametric analysis and non-normally distributed data were compared using nonparametric statistical analyses. Categorical variables were analyzed with the χ^2 exact test and quantitative data were analyzed using the Mann–

Whitney Wilcoxon test with a final two-sided P value of less than 0.05 indicating statistical difference.

SPSS 13.0 software was used.

Central contact:

[name]

National Clinical Research Center for Digestive Diseases; Department of Gastroenterology,

Changhai Hospital, [name]

[contact]

[contact]

E-mail: [name]

Disclosures: The authors declared **no** conflict of interest.

Acknowledgement: None.

REFERENCES

7. Monteiro S, de Castro FD, Carvalho PB et al. PillCam® SB3 capsule: Does the increased frame rate eliminate the risk of missing lesions? *World J Gastroenterol* 2016; 22: 3066-3068.

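### The exact test for the two detection rates is valid but conservative at about 40 per arm; a prespecified Boschloo test would recover some power at little cost

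*Combined protocol and SAP*

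**What the plan says.** The Statistical analysis section states "Categorical variables were analyzed with the χ^2 exact test" and takes a "final two-sided P value of less than 0.05 indicating statistical difference". It does not define the test further. It also says "As a pilot study to evaluate the clinical utility of MCCG-2, sample size was not calculated for this study", so there is no power target and no assumed detection rate.

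Study outcomes and definition lists first among the primary measures the "detection rate of Z-line and duodenal papilla defined as at least one image of Z-line or duodenal papilla was obtained". I read these as two separate yes/no outcomes per patient.

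The Patients section gives a total sample of 80, with the allocation described as "randomly allocated into MCCG-1 group or MCCG-2 group a 1: 1 ratio". Forty per arm follows from 80 at 1:1 but is not written. On method, "The randomization schedule was generated by the investigator using a random number table"; no blocking is described.

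**The concern.** A conditional exact test on a 2 x 2 table fixes the total number of detections. At this sample size only a few P values are then possible, and the largest one below 0.05 is often well below it. The rule of rejecting at P below 0.05 therefore uses only part of the permitted error.

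The number of patients is fixed without a power calculation, so the choice of test is one of the few remaining ways to gain power. At stake is whether a real difference in Z-line or papilla detection is reported as no difference when another exact test, with error still at or below 5%, would have found it.

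**Working it through.** **Inputs from the documents.** 80 patients, 1:1, hence 40 and 40 if perfectly balanced; two-sided threshold 0.05; two yes/no outcomes. The plan has no computed figure to reproduce.

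**Assumptions.** The phrase means a conditional exact test (Fisher, or chi-square with exact P; with equal arms the two give identical P values). Detection rates are assumed, because none are given.

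**Hand check of the discreteness.** Suppose all non-detections fall in one arm of 40, with none in the other.
- 35/40 vs 40/40: P = 2 × C(40,5)/C(80,5) = 2 × 658,008/24,040,016 = 0.055. This is not significant, so with five misses in total the test cannot reject at all.
- 34/40 vs 40/40: P = 2 × C(40,6)/C(80,6) = 2 × 3,838,380/300,500,200 = 0.026.

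**Size.** For a common rate p, sum over all 41 × 41 tables: size(p) = Σ b(x; 40, p) · b(y; 40, p) over tables with P < 0.05, where b is the binomial probability.

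| Common rate | Size of conditional exact test, 40/40 |
|---|---|
| 50% | 3.3% (maximum) |
| 75% | 2.9% |
| 90% | 1.7% |
| 95% | 0.4% |

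The maximum over all rates rises when the arms are unequal: 4.2% at 39/41, 4.4% at 38/42 and 4.3% at 36/44.

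**Boschloo's test.** Order the tables by conditional P and reject when that P is at or below a cut c, the largest value for which the maximum of size(p) over p stays at or below 0.05. At 40/40, c = 0.0707 and the maximum size is 4.77%. Because c exceeds 0.05, every conditional rejection is kept. Another 44 tables are added, among them 35/40 vs 40/40. At the unequal splits checked, the maximum size is at most 4.9%.

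**Power.** The same sum is taken with rates p1 and p2 in the two arms.

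| Assumed rates | Conditional exact, 40/40 | Boschloo, 40/40 | Gain (points) | Gain at nearby unequal splits (points) |
|---|---|---|---|---|
| 30% vs 60% | 72.5% | 76.4% | 3.9 | 0.2-0.4 (39/41, 38/42) |
| 20% vs 45% | 58.6% | 65.8% | 7.2 | 2.4-6.7 |
| 75% vs 95% | 64.6% | 70.2% | 5.6 | about 3-7 |
| 80% vs 97.5% | 60.1% | 69.5% | 9.4 | 0.9-10.5 |

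The ranges in the last column depend on the split and on which arm is larger. On a 0.05 grid of rate pairs at 40/40, the gain is 2.6 to 8.0 points where conditional power is 50-80%, and at most 1.9 points where it exceeds 90%. Over all pairs scanned it runs from 0 to about 13 points; the top is near the ceiling (85% vs 98%: 36.3% to 49.4%).

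**Familywise error for the two rates, if independent:** 1 − (1 − α)².
- Conditional test: α = 2% gives 4.0%; α = 3.3% gives 6.5%.
- Boschloo: α = 4.15% gives 8.1%; α = 4.77% gives 9.3%.

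**The case against.** A reader might infer that the trial misstates its error rate. The documents do not support that. They set a decision threshold for P and promise no achieved error of 5%; a test whose size is below its threshold is valid. No power is promised either, so no stated figure is contradicted. This objection stands in full and makes the point one of efficiency.

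A reader might also infer that 4-9 points of power are lost in this trial whatever happens. That too is unsupported. The rates are assumptions, and the figures are for a perfect 40/40 split. With simple randomization that split has probability C(80,40)/2^80, about 9%, and one unusable recording would also break it. Off 40/40 the deficit shrinks, and for 30% vs 60% the gain nearly vanishes. Other pairs keep a real gain, so the objection bounds the point without removing it.

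The wording of the test is ambiguous. If ordinary Pearson chi-square was meant, size at 40/40 is 4.3-5.9% for rates of 5-95%, and there is no conservatism to recover. Boschloo's test would then cost power (75% vs 95%: Pearson 76.3%, Boschloo 70.2%) and would buy a guarantee that size stays at or below 5%. The power gain therefore depends on the literal exact reading.

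Finally, conditional exact testing is conventional, and a less conservative test on two unadjusted outcomes uses more familywise error. That cost is real and belongs in the fix.

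**Conclusion.** This is a cheap improvement and not an error. Under the conditional exact reading, the planned test has a true size of at most 3.3% at 40/40 and at most about 4.2-4.4% at 39/41 or 38/42. Boschloo's test stays at or below 5% and is never less powerful than the conditional test. For the four assumed mid-power pairs it gains about 4-9 points at 40/40 and about 0-10 points at nearby splits. Closer to the ceiling the gain can be larger; where power is already above 90% it is negligible.

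The conclusion rests on the literal reading of the test's name, on near-equal arms and on assumed detection rates. The severity is low.

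**What to change.** In Statistical analysis, name the 2 x 2 test explicitly. Before group results are known, prespecify Boschloo's unconditional exact test, two-sided at 0.05, for Z-line detection and for papilla detection, with the conditional exact P value reported alongside. The document describes enrolment in the past tense; if group results are already known, report Boschloo's test only as a sensitivity analysis, since switching then to a test that rejects more often would be post hoc.

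Add a sentence on multiplicity for the two rates: either a rule that controls the familywise error, or a plain statement that each is tested at 0.05 and that the joint error is about 8-9% if they are independent.

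The cost is two or three sentences in the plan and, if SPSS 13.0 does not offer the test, a short run in R or Python. No patients are added, and no result significant under the conditional test is lost at the same threshold. A multiplicity rule, if adopted, would use up part of the power gained.
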